We're following up about your participation in a VA research study. It's time to schedule our final meeting so we can update you on our progress. Please use the following link to show when you are available for this meeting. If you have any trouble with the scheduling link or would like speak with a study team member you can email us at [contact] or contact us at XXX-XXX-XXXX.

We cannot guarantee email is secure so please do not reply back to this message with any personal information or personal health information.

Thank you and have a great day!

3. Email script 2 for EAP scheduling

Subject: research study follow up

Hello,

We're following up about your participation in a VA research study. Based on everyone's availability, we are hoping to schedule the meeting for DATE at TIME. The meeting will take place at LOCATION (phone/telehealth/in person). Please reply YES or NO to this email to confirm this works for you. If you had any trouble with the scheduling link or would like speak with a study team member you can email us at [contact] or contact us at XXX-XXX-XXXX. We cannot guarantee email is secure so please do not reply back to this message with any personal information or personal health information.

Thank you and have a great day!

Aim 3 quantitative data will be collected at baseline, post-RCT participation, and 3 month and 6 month follow-up and qualitative data will be collected at 3 month or 6 month follow-up. Feasibility will be assessed with study administration data on engagement and participation in the intervention and preliminary efficacy will be evaluated via coded Veteran/provider encounters and quantitative analysis of functioning from self-report surveys. Further needed intervention modifications will be identified from qualitative interviews.

Participants will have the option of completing the surveys in person, by phone, or by mail. If participants completing the surveys by mail have not returned the surveys within one week a study team member will follow-up by phone. Participants completing the surveys by phone or mail will be mailed their participation compensation upon receipt of the survey data.

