The primary goal of the Aim 3 pilot RCT is to assess the feasibility of PCI for a larger confirmatory RCT. After considering time and resources available with this CDA-2, we believe it will be feasible to randomize 24 individuals per condition. We expect 20% of those randomized in each condition will miss data collection at TP3, and 30% at TP4. This sample size will not be sufficient to detect "small" clinically important differences at TP3 (post-treatment) with 80% power as would be expected of a larger confirmatory RCT. However, with the anticipated 19 participants per condition with complete data at TP3, power is estimated to be equal to .80 for detecting between "medium" and "large" effect sizes ($d=.65$) with the ANCOVA analysis, assuming TP1 to TP3 or TP4 correlation in the response variable is $r=0.7$.

2 * Provide the plan for data analysis. Include in the description the types of comparisons that are planned (e.g., comparison of means, comparison of proportions, regressions, analysis of variance, etc.), which is the primary comparison/analysis, and how the analyses proposed will relate to the primary purposes of the study:

Aim 1 data analysis.

Audio recordings of Aim 1 will not be transcribed as outlined in Aim 2. Recorded Veteran-provider encounters will be coded by research staff using the Measure of Patient-Centered Communication (MPCC). Theoretically grounded in Stewart et al.'s model of patient-centered care, the MPCC is a method for trained raters to assess and quantify recordings of patient-provider encounters. It does not necessitate that the recorded encounters be transcribed for coding. The MPCC has been used to code many types of patient/provider encounters including care for acute and chronic conditions, routine physicals, follow-up visits and emergency department encounters.

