In addition we will conduct exploratory analyses using data collected from the RCT examining whether Veteran perception of satisfaction with VA mental health care, therapeutic alliance, and personal agency differ between control and treatment conditions.

Mediation Analyses. As an example, the mediating effect of Personal Agency (from PAM) between the PCI intervention (PCI vs Control) and VR-36 Social Functioning subscale will be based on Sobel's test for an indirect effect. The first step is to test whether there is a total effect (path c'), i.e. a treatment group difference on the Social Functioning subscale at TP3. If there is a significant group difference on Social Functioning, then the second step will be to estimate both the effect of the PCI on Personal Agency (mediation path 'a') and the direct effect of Personal Agency on Social Functioning (mediation path b) when the treatment indicator is also in the model. Sobel's test tests the significance of the product $a \cdot b$ (indirect effect) by using a bootstrap 95% 'bias corrected' confidence interval. Same procedure will be used for other outcomes and mediators.

Moderator Analyses. Moderators will be tested by simply adding the main effect term and interaction term between the moderator and treatment group indicator to the main outcomes analysis model. Moderators must be assessed pre-intervention, hence at baseline. Evidence of moderation is provided if the interaction term is statistically significant. Moderators can be examined for MPCC (TP2), and the health and functioning outcomes (TP3).

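### The mediation plan tests the indirect effect only after a significant total effect at TP3, a condition the test does not need and that discards information at 19 per arm

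*Combined protocol and SAP*

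**What the plan says.** The rule is in Sample Size and Data Analysis, item 2, under Mediation Analyses. The worked example is Personal Agency as mediator of the PCI effect on VR-36 Social Functioning. Step 1 is described thus: "The first step is to test whether there is a total effect (path c'), i.e. a treatment group difference on the Social Functioning subscale at" (the time point named is TP3). Step 2 is conditional on it: "If there is a significant group difference on Social Functioning, then the second step" is taken, which estimates path a (PCI to mediator) and path b (mediator to outcome).

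The product a·b is then tested "by using a bootstrap 95% 'bias corrected' confidence interval", a procedure the text calls Sobel's test. The scope is general: "Same procedure will be used for other outcomes and mediators". Nothing says that a·b will be estimated or reported if step 1 is not significant.

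Item 1 of the same section gives the sample size. It says "we believe it will be feasible to randomize 24 individuals per condition", expects 20% missing data at TP3, and so has 19 per condition for analysis. It states power of 0.80 at d = 0.65 with an ANCOVA and a baseline-to-follow-up correlation of 0.7. It concedes that small differences cannot be detected with 80% power, and it names feasibility as the primary goal of the pilot.

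**The concern.** The total effect is the sum of the indirect effect a·b and the direct effect. The bootstrap interval for a·b rests on its own two regressions and does not use the total-effect test. A condition placed in front of it can therefore only remove results that the data could have supplied. It also ties the mediation analysis to an efficacy test that the plan itself says has limited power.

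At stake is the planned quantitative analysis of how the PCI works. The pilot is meant to inform a larger confirmatory trial, and the VA-Specific Criteria section says later work will refine interventions around mechanisms of change. If step 1 fails, the plan as written provides neither path b nor an interval for a·b to take forward.

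**Working it through.** **Inputs.** From item 1: 24 randomized per arm; 20% missing at TP3, so 24 × 0.8 = 19.2, taken as 19; d = 0.65; r = 0.7; power 0.80. The significance level for step 1 is not stated, so two-sided 0.05 is assumed.

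**Reproducing the plan's power.** Working in outcome SD units:
- Residual SD after baseline adjustment = √(1 − 0.7²) = 0.714.
- SE of the arm difference = 0.714 × √(2/19) = 0.232.
- Power ≈ Φ(d/SE − 1.96). At d = 0.65 this is Φ(2.805 − 1.96) = Φ(0.845) = 0.801.

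This matches the stated 0.80. The noncentral t version with one covariate gives 0.779. The plan's figure is therefore the two-sided normal approximation, which supports the assumed level.

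**How often step 2 is skipped.** Step 1 is this same comparison, so the skip rate for one outcome is 1 minus its power.

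| True total d | Step 1 significant (normal / t) | a·b skipped (normal) |
|---|---|---|
| 0.65 | 80% / 78% | 20% |
| 0.5 | 58% / 56% | 42% |
| 0.4 | 41% / 39% | 59% |
| 0.3 | 25% / 24% | 75% |
| 0.2 | 14% / 13% | 86% |

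The break-even point, where step 2 is reached half the time, is d = 1.96 × 0.232 ≈ 0.45 (0.47 with the t version). With r = 0.5 it is 0.55 to 0.57.

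**What the condition costs in detections.** This was simulated with 19 per arm and r = 0.7. The mediator equals a × arm plus unit-variance noise. The outcome equals 0.7 × baseline, plus the direct effect × arm, plus b × mediator, plus noise. The residual outcome variance given baseline and arm is 0.51. Each scenario used 1,500 trials and 400 bias-corrected bootstrap resamples. Path a and the share mediated are assumptions, and b = share × d / a.

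| Total d | a | Share mediated | Step 1 significant | a·b interval excludes 0, no condition | Same, with condition |
|---|---|---|---|---|---|
| 0.2 | 0.65 | all | 12% | 50% | 8% |
| 0.3 | 0.65 | all | 22% | 57% | 19% |
| 0.4 | 0.8 | all | 37% | 73% | 36% |
| 0.5 | 0.8 | all | 54% | 73% | 52% |
| 0.65 | 1.0 | all | 75% | 87% | 74% |
| 0.3 | 0.65 | half | 25% | 35% | 11% |
| 0.5 | 0.8 | half | 54% | 64% | 38% |
| 0.65 | 0.8 | half | 76% | 74% | 62% |

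The condition loses detections in every row, most at small and moderate effects.

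**False positives without the condition.** Further simulations at 19 per arm set one path to zero. With a = 0, the bias-corrected interval excluded zero in 7.8% to about 9% of trials, and the percentile interval in 5.2% to about 6%. With a = 0.65 and b = 0, one run gave 5.2% against 2.5%. With both paths zero it gave 0.9% against 0.2%. With the condition kept and no total effect, the rate was 0.4–3%. The percentile interval still detected a·b in 49% of trials at a = 0.65, b = 0.4 and 71% at a = 0.8, b = 0.5, against 56% and 75% for the bias-corrected interval.

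**The case against.** Testing the total effect first is a recognised and conservative choice. Mediation belongs to no aim or hypothesis, and feasibility is the primary goal. That limits the importance of the point but gives no reason to keep the condition.

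Four stronger readings are tempting, and the documents do not support them.

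- **That the sample size means mediation will usually go unexamined.** At the plan's own d = 0.65 and r = 0.7, step 2 is reached in about 80% of trials. It is skipped more often than not only if the true d is below about 0.45–0.47, and the documents give no smaller expected effect.
- **That the total-effect test is always the weaker one.** That pattern comes from assuming full mediation. With a = 0.65, b = 0.4 and a direct effect of 0.39 (total 0.26 + 0.39 = 0.65), step 1 was significant in 76–79% of trials and the a·b interval excluded zero in 56–58%. Even there, the condition cut detections of a·b from 56% to 51%.
- **That passing step 1 means the total effect was overestimated.** The mean estimate among passing trials is d + 0.232 × φ(z)/Φ(z), with z = d/0.232 − 1.96. This gives about 0.73 at a true d of 0.65, a modest inflation (0.74–0.75 by simulation). It is severe only at small effects, for example 0.62 when the truth is 0.40.
- **That mechanism is left wholly unexamined.** The exploratory paragraph just before Mediation Analyses compares personal agency, alliance and satisfaction between arms unconditionally. For Personal Agency that is essentially path a. MPCC behaviours at TP2 are also compared without a condition. What is withheld is path b and the a·b interval.

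Mediator timing cannot be pressed either. Study Procedures says "Aim 3 quantitative data will be collected at baseline, post-RCT participation, and 3 month and 6 month follow-up", but the questionnaire list for RCT participants has no visit schedule. Nothing shows that Personal Agency is measured at the post-session visit.

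The objection that dropping the condition raises false positives stands, and the fix must address it.

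**Conclusion.** The point holds in a limited form. The plan conditions the indirect-effect analysis on a significant TP3 total effect, for every outcome and mediator, and that condition is unnecessary. It skips the a·b analysis of a given outcome in about 20% of trials at the design effect, rising to 59–86% for d from 0.4 to 0.2.

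These figures assume two-sided 0.05, 19 complete cases per arm, r = 0.7 and no allowance for provider clustering. They are per outcome: with several subscales, the chance that at least one passes step 1 is higher. The losses in detection also depend on the assumed a, b and share mediated, though their direction was the same in every scenario with a true indirect effect.

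Calling the bootstrap interval Sobel's test misnames the method. That, and labelling the total effect c', are cosmetic because the text defines each quantity. Overall this is a worthwhile wording change to a secondary part of the plan.

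**What to change.** In Mediation Analyses, delete the condition attached to step 1. For each mediator–outcome pair, estimate a, b and a·b with a bootstrap 95% interval whatever the total effect shows, and report the total effect beside them. Adjust for the baseline outcome and, where it is collected, the baseline mediator. Label all of these results exploratory. Call the method a bootstrap test of the indirect effect.

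Use the percentile interval, or keep the bias-corrected one and disclose that at this size it excludes zero in up to about 7–9% of trials when one path is zero, against about 5–6% for the percentile interval.

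The cost is plan wording only, with no new data or visits. Two downsides should be stated: more intervals are reported across mediators and outcomes, and the percentile interval gives up some power (49% against 56%, and 71% against 75%, in the two scenarios checked).

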1 * Select all behavioral methods and procedures which apply to this study:

- Surveys/questionnaires
- Key informant or semi-structured individual interviews
- Focus groups or semi-structured group discussions
- Audio or video recording/photographing
- Educational tests or normal educational practices (education instructional strategies, techniques, curricula, or classroom management methods)
- Individual or group behavioral observations
- Psychosocial or behavioral interventions**
- Neuropsychological or psychophysiological testing
- Deception
- Other psychosocial or behavioral procedures

ID: VIEW4E09416F57800
Name: v2_Psychological/Behavioral/Educational Methods and Procedures

Surveys/Questionnaires

You indicated that this study involves surveys and/or questionnaires.

If you uploaded a separate research protocol document in the 'Research Protocol' page, cite the applicable section and page numbers from that document in the answer boxes below.

1 * List all questionnaires/surveys to be used in the study, including both standardized and non-standardized assessments:

1. Demographics Form - Veteran
2. Demographics Form - Provider
3. Consultation Care Measure
4. Perceived Involvement in Care Scale
5. Working Alliance Inventory-Client
6. Veterans RAND 36 Item Health Survey
7. World Health Organization Disability Assessment Schedule
8. Depression Anxiety Stress Scale
9. PTSD Checklist for DSM-5
10. Alcohol Use Disorders Identification Test-C
11. Drug Abuse Screening Test
12. Patient Activation Measure for Mental Health
13. Client Satisfaction Questionnaire
14. Patient Participation subscale of the Patient Empowerment Scale

For RCT participants

1. Demographics Form - Veteran
2. World Health Organization Disability Assessment Schedule 2.0
3. Veterans RAND 36 Item Health Survey
4. Alcohol Use Disorders Identification Test-C
5. Drug Abuse Screening Test
6. Depression Anxiety Stress Scale
7. PTSD Checklist for DSM-5
8. Mental Health Confidence Scale
9. Consultation Care Measure
10. Perceived Involvement in Care Scale
11. Patient Participation subscale of the Patient Empowerment Scale
12. Patient Activation Measure for Mental Health
13. Patient Activation Measure for Physical Health
14. Working Alliance Inventory-Client
15. Client Satisfaction Questionnaire
16. Technology Use Survey
17. Intervention Material Utilization (Omnis Salutis Utilization or Health and Wellness Utilization)
18. COVID Questionnaire

2 * Upload a copy of all questionnaires/surveys:

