- If meeting face-to-face with a veteran for their individual session(s) is not possible then a trained study interventionist may (1) transport a study audio recorder to capture the audio of any individual session(s) completed via telehealth visit or (2) utilize the VA's protocol for Recording in CAG using Audacity Application and will export the recording to a restricted access VA sharedrive. If the interventionist uses an audio recorder they will utilize their locked HIPAA bag to transport the recorder, to ensure its protection.

- If meeting face-to-face with a veteran for their regularly scheduled mental health care is not possible and the veteran has provided consent to record one of their regularly scheduled mental health care appointments, then the study team will approach the veteran's mental health care provider to ask if they are willing to utilize the VA's protocol for Recording in CAG using Audacity Application. If they agree then the study team will make arrangements with the clinician to receive the recording via a sharedrive and immediately export the recording to a restricted access VA sharedrive.

Behavioral Intervention

You indicated that this study involves psychosocial or behavioral interventions.

1 * Describe the intervention (duration, number of sessions, focus, etc.):

Aim 3

Treatment condition. We anticipate that the person-centered intervention (PCI) will be comprised of three, one-hour sessions offered over three to six weeks, scheduled at the participants' preference. Sessions will be one-on-one with the interventionist. The PCI sessions will be offered in a private room in the same buildings that VA mental health services are located in, on the two respective VAMHCS campuses OR will be offered via VA Video Connect, the VA's telehealth program which uses encryption to ensure a secure and private session, OR phone.

Control condition. The control condition will be an educational health and wellness intervention for stress related disorders that will match the experimental condition for time and attention. The control condition will be three, one hour, individual sessions covering the symptom cycle, managing stress, and identifying social supports. The interventionist will be a non-blinded member of the research team such as the

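### The exploratory mediation procedure leaves path b open to pre-existing correlation: no baseline terms, no mediator time point and no PAM form are stated

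*Combined protocol and SAP*

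**What the plan says.** The worked example in Mediation Analyses concerns "the mediating effect of Personal Agency (from PAM) between the PCI intervention" and the VR-36 Social Functioning subscale. It has two steps.

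- Step 1 tests the total effect, defined as "a treatment group difference on the Social Functioning subscale at TP3".
- Step 2 is conditional: "If there is a significant group difference on Social Functioning, then the second step will be to estimate both" path a and path b. Path b is "the direct effect of Personal Agency on Social Functioning (mediation path b) when the treatment indicator is also in the model". The product of the paths is judged by a bias-corrected bootstrap interval.

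The outcome therefore has an occasion (TP3) and the mediator has none. No TP1 value of PAM or of Social Functioning is named in either path. The paragraph then extends the procedure to the other mediators and outcomes. The next paragraph does set a timing rule, but for moderators only: "Moderators must be assessed pre-intervention, hence at baseline".

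In Surveys/Questionnaires, item 1, the RCT battery contains the mental health PAM and also the "Patient Activation Measure for Physical Health". The mediation text says only PAM.

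**The concern.** PCI is randomised, so the arm difference in PAM (path a) is protected. PAM itself is not randomised. Path b is an observational association within arms between two self-reports from the same people. Veterans who were more activated and better functioning before the trial will tend to be so afterwards. Without their starting values in the model, that persistence loads onto path b. Multiplied by a real path a, it gives a non-zero indirect effect even when activation does nothing to functioning.

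The open time point adds a second route: if both scales come from the same visit, shared reporting on the day also enters path b. The open PAM form leaves a choice that could be made after seeing the data. Because the procedure is reused for every mediator and outcome, so is the weakness.

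**Working it through.** **The plan's own figure.** Mediation has no stated figure. The sample-size figure reproduces: with d = 0.65, 19 per arm, r = 0.7 and two-sided alpha 0.05 (assumed; not stated), 0.65 / [√(1 − 0.49) × √(2/19)] = 0.65 / 0.2317 = 2.805. Power is Φ(2.805 − 1.960) = 0.801, against 0.80 stated. The sample-size statement is not at issue.

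**Inputs.** From the plan: stability 0.7 (stated for the response variable; applying it to PAM is an assumption), 19 per arm at TP3, total effect 0.65 SD. Not in the documents, so assumed: the PAM–Social Functioning correlation and path a. The true effect of PAM on Social Functioning is set to zero throughout. Scores are in within-arm SD units.

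**Model A: correlated at baseline (ρ), independent changes afterwards.** Each follow-up score is 0.7 × its TP1 value plus independent noise. Within arm, Cov(M, Y) = 0.7 × 0.7 × ρ and Var(M) = 1. With only mediator and arm in the model, b = 0.49ρ. Once TP1 Social Functioning is added, the remaining variation in Y is noise unrelated to PAM, so b = 0.

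**Model B: stable shared trait.** Each scale correlates 0.7 with itself over time, and every PAM–Social Functioning correlation equals x, within or across occasions.

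- Terms as written: b = x
- Baseline outcome added: b = 0.3x / (1 − x²)
- Both baselines added: b = 0.3x / (1.7 − 2x²)

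| Model and correlation | As written | Baseline outcome | Both baselines |
|---|---|---|---|
| A, 0.3 | 0.147 | 0 | 0 |
| A, 0.4 | 0.196 | 0 | 0 |
| A, 0.5 | 0.245 | 0 | 0 |
| B, 0.3 | 0.30 | 0.09/0.91 = 0.10 | 0.09/1.52 = 0.06 |
| B, 0.5 | 0.50 | 0.15/0.75 = 0.20 | 0.15/1.20 = 0.13 |

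With path a = 0.65 SD, Model A as written gives a spurious indirect effect of 0.65 × 0.147 = 0.10 to 0.65 × 0.245 = 0.16 SD.

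**Error rates at the planned size.** Model A was simulated with 19 per arm, path a and total effect both 0.65 SD, 1,000 trials, and a bias-corrected bootstrap with 600 resamples. The table shows the share declaring mediation when there is none.

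| ρ | As written | As written, total effect significant | Baseline outcome | Both baselines |
|---|---|---|---|---|
| 0.3 | 14% | 15% | 7% | 8% |
| 0.5 | 24% | 24% | 5% | 8% |
| 0.7 | 40% | 41% | 6% | 7% |

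The total-effect test was significant in 75% to 79% of these trials. If PCI does not move PAM (a = 0, ρ = 0.5), false mediation falls to 4.5%.

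**Same-visit measurement.** With ρ = 0.5 and an assumed residual correlation of 0.4 between the two scales at the visit, false mediation is 53% as written, 34% with baseline outcome, and 65% with both baselines. Baseline adjustment does not substitute for an earlier mediator.

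**The case against.** **Hypothesis 3b already adjusts for baseline.** Step 1 is a TP3 comparison on a VR-36 subscale, which hypothesis 3b analyses by ANCOVA with baseline adjustment. The path b wording says the treatment indicator is also in the model, not that nothing else is. If that adjustment carries over, the Model A bias disappears. This stands as far as it goes. However, the mediation paragraph does not refer to that model, whereas the moderator paragraph does refer to the main outcomes model. The carried-over term would not include baseline PAM, and under Model B 0.10 to 0.20 remains.

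**The total-effect gate limits the damage.** This is correct when the effect is small. A simulation with 19 per arm, a = 0.5, ρ of 0.3 to 0.5 and 300 trials gave these results for the terms as written. With a true total effect of 0.3 SD, the gate passed about 20% of the time, and gate plus false mediation occurred in 1% to 2% of trials. At 0.65 SD the joint rate was 9% to 17%. Among trials that pass the gate it gives no protection.

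**Stronger readings that the documents do not support.** A reader might infer that mediator and outcome are measured at the same visit; the text leaves the timing open and does not say so. A reader might also infer that the physical-health PAM could rise in the control arm and reverse path a. The control is an "educational health and wellness intervention for stress related disorders" covering the symptom cycle, stress management and social supports, with no physical-health content listed, so nothing supports a reversal. Context favours the mental health form, since personal agency is listed beside satisfaction with mental health care and therapeutic alliance.

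**This is exploratory work in a feasibility pilot.** It is, and that limits the weight of the point. Targeting mechanisms of change appears in VA-Specific Criteria, item 1, as a goal of later studies; the documents do not say that this mediation result will set the next trial's target.

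**Conclusion.** The point holds as a correctable weakness in an exploratory analysis. As described, path b does not separate an effect of activation on functioning from correlation that was there before randomisation. The mediator's occasion and form are also left open.

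With no causal effect, and under assumed correlations of 0.3 to 0.5 and stability of 0.7 for both scales, path b is 0.15 to 0.25 SD with the terms as written (Model A). Baseline-outcome adjustment would remove that. Under a stable shared trait, 0.10 to 0.20 remains with baseline outcome alone and 0.06 to 0.13 with both baselines, so the full remedy reduces the bias without guaranteeing its removal.

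A false finding depends on PCI moving PAM and on a significant total effect. The correlations and path a are assumptions; the documents give neither. The primary comparisons and the stated power are unaffected.

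**What to change.** Amend the Mediation Analyses paragraph as follows.

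1. Include the TP1 mediator and TP1 outcome in both the path a and path b models, for every mediator–outcome pair.
2. Name the mental health PAM as the mediator form.
3. Take the mediator at an occasion before the outcome: TP2 then TP3 if PAM is collected at TP2, otherwise TP3 then TP4, with the total-effect step restated for the occasion used.
4. Label the results hypothesis-generating, because some shared-trait bias can remain.

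Item 3 has to be conditional. Study Procedures, item 1, lists four occasions, with a post-participation one before the 3-month visit. But the sample-size text calls TP3 post-treatment, hypothesis 3b ties only the MPCC to TP2, and no section says when PAM is given. The schedule should be stated first.

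**Cost.** A few sentences of analysis text, with no new data if PAM is collected at the chosen occasion. The models gain one or two covariates with about 19 per arm. The TP3-then-TP4 route accepts the planned 30% missing at TP4 (24 × 0.7 = 16.8 per arm). Power for the total effect at d = 0.65 is then about 0.73 to 0.76 with 16 or 17 per arm.
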